## 6.3 Recording and reporting of Adverse Events

Investigators will seek information on AEs during each patient contact. All events, whether reported by the patient or noted by the Investigation staff, will be recorded in the patient's medical record and in the (e)CRF within a reasonable time after becoming aware. If available, the diagnosis should be reported on the AE form, rather than the individual signs or symptoms. If no diagnosis is available, the Investigator should record each sign and symptom as individual AEs using separate AE forms.

The following minimum information should be recorded for each AE:

- AE description
- start and stop date of the AE
- severity
- seriousness
- causality assessment to the IMD and/or Investigation procedures
- outcome

### 6.3.1 Assessment

All AEs must be evaluated by an Investigator as to:

- **Seriousness:** whether the AE is an SAE. See above for the seriousness criteria.
- **Severity:**
  - Severity must be evaluated by an Investigator according to the following definitions:
    - *Mild* – no or transient symptoms, no interference with the subject’s daily activities
    - *Moderate* – marked symptoms, moderate interference with the subject’s daily activities
    - *Severe* – considerable interference with the subject’s daily activities, unacceptable
- **Causality:**

Not related	
Relationship to the device, comparator or procedures can be excluded when:
 
 
- the event has no temporal relationship with the use of the IMD, or the procedures related to application of the IMD;
 
- the SAE does not follow a known response pattern to the medical device (if the response pattern is previously known) and is biologically implausible;
 
- the discontinuation of medical device application or the reduction of the level of activation/exposure – when clinically feasible – and reintroduction of its use (or increase of the level of activation/exposure), do not impact on the SAE;
 
- the event involves a body-site or an organ that cannot be affected by the device or procedure;
 
- the SAE can be attributed to another cause (e.g., an underlying or concurrent illness/ clinical condition, an effect of another device, drug, treatment or other risk factors);
 
- the event does not depend on a false result given by the IMD used for diagnosis, when applicable.
 
 
In order to establish the non-relatedness, not all the criteria listed above might be met at the same time, depending on the type of device/procedures and the serious adverse event.

Possible	
The relationship with the use of the IMD or comparator, or the relationship with procedures, is weak but cannot be ruled out completely. Alternative causes are also possible (e.g., an underlying or concurrent illness/ clinical condition or/and an effect of another device, drug or treatment). Cases where relatedness cannot be assessed, or no information has been obtained should also be classified as possible.

Probable	
The relationship with the use of the IMD or comparator, or the relationship with procedures, seems relevant and/or the event cannot be reasonably explained by another cause.

Causal relationship	
The SAE is associated with the IMD, comparator or with procedures beyond reasonable doubt when:
 

- the event is a known side effect of the product category the device belongs to or of similar devices and procedures;

- the event has a temporal relationship with IMD use/application or procedures;

- the event involves a body-site or organ that

• the IMD or procedures are applied to;

• the IMD or procedures have an effect on;

- the SAE follows a known response pattern to the medical device (if the response pattern is previously known);

- the discontinuation of medical device application (or reduction of the level of activation/exposure) and reintroduction of its use (or increase of the level of activation/exposure), impact on the SAE (when clinically feasible);

- other possible causes (e.g., an underlying or concurrent illness/clinical condition or/and an effect of another device, drug or treatment) have been adequately ruled out;

- harm to the subject is due to error in use;

- the event depends on a false result given by the IMD used for diagnosis, when applicable;

 
In order to establish the relatedness, not all the criteria listed above might be met at the same time, depending on the type of device/procedures and the SAE.

----------------------------	--

### 6.3.2 Timelines for reporting

- After informed consent has been obtained, but prior to first use of the IMD, only AEs caused by an Investigation specific procedure should be reported
- After first use of the IMD, AEs will be reported as follows:
  - o All AEs, SAEs, and DDs will be reported until 7 days after last use of the IMD, or until last follow-up visit (whichever occurs first).

All SAEs as defined in the CIP must be reported to the Sponsor within 24 hours of the investigation staff becoming aware of the event. The immediate report shall be followed by detailed, written reports. The immediate and follow-up reports shall identify subjects by code numbers.

SAE details will be reported by the Investigator to the Sponsor:

- By completing the SAE form in the (e)CRF

If an authorised Investigator from the reporting site is unavailable, initial reports without causality assessment should be submitted to the Sponsor by a healthcare professional within 24 hours of becoming aware of the SAE, but must be followed-up by medical assessment as soon as possible thereafter.

### 6.3.3 Follow-up

The Investigator must record follow-up information by updating the patient's medical records and the appropriate forms in the (e)CRF. The worst case severity and seriousness of an event must be kept throughout the Investigation.

SAE follow-up information should only include new (e.g., corrections or additional) information and must be reported within 24 hours of the Investigator's first knowledge of the information. This is also the case for previously non-serious AEs which subsequently become SAEs.

- All SAEs must be followed up until the outcome of the event is 'recovered', 'recovered with sequelae', 'not recovered' (in case of death due to another cause) or 'death' (due to the SAE) and until all related queries have been resolved, or until end of the Investigation (whichever occurs first).

- *Non-serious AEs* must be followed up until the patient's last study visit, and until all related queries have been resolved.

**SAEs after the end of the Investigation:** If the Investigator becomes aware of an SAE with suspected causal relationship to the IMD or experiment after the subject has ended the Investigation, the Investigator should report this SAE within the same timelines as for SAEs during the Investigation.

#### 6.3.4 Pregnancy

Female subjects must be instructed to notify the Investigator immediately if they become pregnant during the Investigation.

#### 6.3.5 Death

All deaths will be reported without delay to the Sponsor (irrespective of whether the death is related to disease progression, the IMD, study procedure or is an unrelated event). The Sponsor will notify all deaths as soon as possible after becoming aware to the EC and provide additional information if requested.

### 6.4 Recording and reporting of Device Deficiencies

**Each DD must be documented by the Investigator in the source documents and reported to the Sponsor on a Device Deficiency form.**

If the DD leads to the occurrence of a (S)ADE, the (S)ADE must also be reported by the Investigator to the Sponsor on the appropriate forms and within the specified timelines.

### 6.5 Reporting requirements to Ethics Committee's (EC's) and Competent Authorities (CA's)

The Investigator is responsible for ensuring that all safety events are recorded in the (e)CRF and reported to the Sponsor in accordance with instructions provided below.

The Sponsor will promptly evaluate all SAEs and DDs against medical experience to identify and expeditiously communicate possible new safety findings to Investigators, ECs and applicable CA's based on applicable legislation.

#### 6.5.1 Sponsor's reporting of Serious Adverse Events and Device Deficiencies

The Sponsor is responsible to report to the CA's where the Investigation has commenced:

- Any SAE that has a **causal** relationship with the IMD, the comparator or the investigation procedure or where such causal relationship is reasonably possible;
- Any DD that might have led to a SAE if:
  - a) Appropriate action had not been taken, or
  - b) Intervention had not occurred, or
  - c) If circumstances had been less fortunate;
- New findings/update in relation to already reportable events.

These 'reportable events' must be reported within the following timelines:

- A reportable event which results in imminent risk of death, serious injury, or serious illness that requires prompt remedial action for other patients/subjects, users or other persons or a new finding to it must be reported immediately, but not later than **2 calendar days** after awareness by the Sponsor of a new reportable event or of new information in relation with an already reported event.
- Any other reportable event or a new finding/update to it must be reported immediately, but not later than **7 calendar days** following the date of awareness by the Sponsor of the new reportable event or of new information in relation with an already reported event.

### 6.5.2 Annual reporting

The Sponsor has the obligation to, once a year throughout the Investigation (or on request), submit a progress report to the EC's and CA's containing an overview of all SAEs occurred during the reporting period and taking into account all new available safety information received during the reporting period.

### 6.5.3 Overview reporting requirements

	WHAT	HOW	TO	TIMELINES
Investigator	AE	AE form	Sponsor	as defined in CIP
	SAE	SAE form	Sponsor	asap, but no later than 3 calendar days after awareness
	DD	DD form + AE/SAE form (if applicable)	Sponsor	as defined in CIP (exception: within 3 calendar days if considered reportable event)
	Death	SAE form	Sponsor	asap
Sponsor	all reportable events (of all participating sites)	EU SAE report form (excel) 	- CA for Belgium - > FAGG: via mail to [contact]	asap, but no later than 2 calendar days (in case of risk of death or serious injury/illness that requires prompt remedial action for other patients, users or other persons)  7 calendar days (all other reportable events)
	Death	SAE form + narrative	- EC	asap
	Annual Progress Report	APR template	- EC - CA for Belgium - > FAGG: via Common European Submission Portal (CESP)	annually

 The SAE report form in Excel format can be downloaded from the following web page: [https://ec.europa.eu/health/sites/health/files/md\\_sector/docs/md\\_mdcg\\_2020-10-2\\_guidance\\_safety\\_report\\_form\\_en.xlsx?web=1](https://ec.europa.eu/health/sites/health/files/md_sector/docs/md_mdcg_2020-10-2_guidance_safety_report_form_en.xlsx?web=1)

### 6.6 Data Safety Monitoring Board (DSMB)

Not applicable

## 7 Statistics and Data Analysis

Statistical analysis will be performed in accordance with ICH E9; a detailed description of the analysis is provided in the study-specific Statistical Analysis Plan (SAP). ICH E3 and E8 will guide the structure and content of the clinical study report.

The statistical analysis for the clinical investigation will be outsourced to a licensed medical statistician (Ars Statistica).

A pseudonymized Excel-export will be generated from the eCRF for statistical analysis.

### 7.1 Sample Size Determination

120 eyes in 2 cohorts

.

### 7.2 Statistical Analysis

#### 7.2.1 Efficacy Analysis

All endpoints: For group comparisons, continuous data will be compared by means of T-test/ANOVA when homogeneity of variances, tested with the Bartlett's test, and normality of the residuals, tested with the Shapiro-Wilks test, will be reached and means and standard deviations (means  $\pm$  StDev) will be reported. When homogeneity of the variance or normality of the residuals will not be proved, Wilcoxon signed rank/Kruskal-Wallis test will be performed on rank data and medians and inter-quartile ranges (median [Q25 – Q75]) will be reported. Next, the dependence between two continuous variables will be studied through Pearson's correlation. Last, for count data, the Pearson Chi-Squared test will be performed to compare proportions.

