## CIP SYNOPSIS

Title of clinical Investigation («Investigation»)	Title: ZEISS RESIGHT Disposable Lenses evaluation study
CIP Short Title Acronym	RESIGHT Disposable
Sponsor name	<University Hospitals Leuven (UZ Leuven) or KU Leuven>
Coordinating Investigator	[name]
Contact Address CI	UZ Leuven, [name]
Contact Email CI	[contact]
Contact Phone CI	[contact]
SIN number	CIV-23-02-042213
Other public database number	not applicable
Principal Investigators and Participating Sites	not applicable
Medical condition or disease under investigation	-Macular pathology requiring surgery: macular pucker, macular hole, vitreomacular traction -Retinal detachment
Study rationale	See row below
Primary objective	To evaluate the intra-operative efficacy of a new intra-operative viewing device.
Secondary objective(s)	/
Clinical Investigation Design	Investigator-initiated, mono-center, academic, prospective, interventional case study
Endpoints	To determine the effectiveness of the device compared to the reusable RESIGHT lenses and Vitreq contact lens presently used as standard-of-care.
Sample Size	120 eyes in two cohorts (60 in each cohort)
IMD	Disposable RESIGHT lenses
Comparator device(s)	Reusable RESIGHT lenses and Vitreq contact lens
Maximum duration of treatment of a Participant	Total inclusion time of each patient is surgery time (from first incision till removal of vitrectomy cannulas)
Maximum duration of the Investigation	Total inclusion time of each patient is surgery time (from first incision till removal of vitrectomy cannulas)
Anticipate First Patient First Visit (FPFV)	Q1 2023
Anticipate Last Patient Last Visit (LPLV)	Q4 2023
Third Parties	Carl Zeiss Meditec AG, [name]; Grant

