#### 7.2.2 The level of statistical significance

The statistical significance level will be 5%

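### Bartlett and Shapiro-Wilk pretests decide what is tested and reported for continuous endpoints, although equal variance is irrelevant to a within-eye comparison and neither route estimates the lens difference

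*Combined protocol and SAP*

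**What the plan says.** Section 7.2.1 opens with "All endpoints: For group comparisons" and gives one rule for continuous data. The parametric route applies conditionally: "continuous data will be compared by means of T-test/ANOVA when homogeneity of variances, tested with the Bartlett's test"; the second condition is a Shapiro-Wilk check on the residuals. Means and standard deviations are then reported. The alternative reads: "When homogeneity of the variance or normality of the residuals will not be proved, Wilcoxon signed rank/Kruskal-Wallis test will be performed on rank data". On that route the summary becomes the median with its quartiles. Failing either pretest is enough to change route.

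The section does not state the level of the pretests, whether the t-test is paired, any unequal-variance method, or any effect estimate with a confidence interval. Section 7.2.2 sets the significance level at 5% without saying whether tests are one- or two-sided. The synopsis gives "120 eyes in two cohorts (60 in each cohort"), with no effect size, SD or power.

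Section 2.1 has both lenses mounted on the rotating arm so that the surgeon can switch between them during one operation. The two cohorts in sections 2.3 and 4.3 are defined by surgical indication, not by lens.

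**The concern.** There are four difficulties.

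- **The target moves with the data.** A t-test concerns a mean difference. A signed-rank test concerns the location of the differences on a rank scale. When the differences are skewed these are different quantities, and the pretests decide which one the report is about.
- **Bartlett's test checks a condition that is not needed.** A paired t-test uses only the within-eye differences, so the spread of each lens's readings may differ freely. Bartlett's test also assumes independent samples, which two readings from one eye are not. If the new lens gave more consistent readings, as a clean optical surface might, that benefit alone could change the analysis.
- **A pretest cannot establish its assumption.** The text speaks of assumptions being proved, but a non-significant result only means that no departure was detected.
- **No effect size results from either route.** Mean and SD, or median and quartiles, describe each lens. A reader who wants to know how much less light or fogging the new lens brings, and how precisely this is known, gets no answer.

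**Working it through.** The plan gives no figure to reproduce, so the rule itself was checked. From the documents: n = 60 per cohort, 5% level, the two-pretest rule, the within-eye comparison. Assumed: pretests at 5%, two-sided tests, and all distributions. Simulations used 3,000 to 4,000 runs per setting. At a true 5%, the error with 3,000 runs is ±1.96 × √(0.05 × 0.95/3000) = ±0.8 percentage points.

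**1. How often Bartlett's test diverts a valid paired t-test.** For normal data the log ratio of two independent sample variances has SE of about √(4/(n − 1)) = √(4/59) = 0.260. Bartlett's test then fires when the log ratio exceeds about 1.96 × 0.260 = 0.510.

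- SD ratio 0.77 (1:1.3): the true log variance ratio is ln(1.69) = 0.525. The chance of firing is about Φ((0.525 − 0.510)/0.260) = Φ(0.06), or 52%. Simulation gives 51 to 53%. With Shapiro-Wilk added, the t route was kept in 44.7% of runs.
- SD ratio 0.5 (1:2): ln(4) = 1.386, so Φ((1.386 − 0.510)/0.260) = Φ(3.4), above 99.9%. In simulation the t route was kept in 0.0% of runs.
- Normal pairs with equal SDs: the t route was kept in 92.2%, so about 8% of comparisons change route with nothing wrong.

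**2. What the diversion costs with normal data.** At SD ratio 0.5 the rule rejects 4.9 to 5.3% under no difference, against 4.6 to 5.3% for the paired t-test. At an assumed shift of 0.4, power is 75 to 76% under the rule and 76.5 to 78% for the paired t-test.

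**3. No difference between lenses (exchangeable readings).** The within-eye differences are then symmetric, even when the readings are skewed. The rule rejects 4.6 to 5.3%, and the paired t-test 4.4 to 5.2%.

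**4. Skewed differences with mean exactly zero.** These are centred gamma differences with shape 1, 2, 4 and 10 and skewness 2/√shape.

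| Skewness | Two-step rule rejects | Paired t-test rejects |
|---|---|---|
| 2.0 | about 26% | 6.8% |
| 1.4 | about 15% | 5.3 to 5.5% |
| 1.0 | 9 to 10% | 5.0 to 5.6% |
| 0.6 | 6 to 7% | 4.7 to 5.3% |

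At skewness 0.6 the t route is taken in 59 to 60% of runs.

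These differences have mean zero but not median zero. For shape 1 the median is ln 2 − 1 = −0.31 SD; for shapes 2 and 4 it is −0.23 and −0.16 SD. The rank route is detecting that shift. The table therefore shows two routes answering different questions.

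**The case against.** **Type I error.** A reader might infer from the table that the rule inflates false positives in general. The documents do not support that. Those rates apply only when the null hypothesis is a zero mean with skewed differences. If the lenses perform alike, the rule holds its level (step 3), and the diversion costs one or two points of power with normal data (step 2). This objection stands and limits the point to the undefined target.

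**Hidden effects.** A reader might also infer that median reporting would conceal a lens effect on fogging. Take assumed grades 0 to 3 with shares 60/20/12/8% for the present lens and 85/10/4/1% for the new lens. The sample medians agree in 92% of runs while the test rejects in 90%. But quartiles are reported too. The upper quartile is grade 1 for the present lens (cumulative 60%, then 80%) and grade 0 for the new one (85% at zero), so the typical report is 0 [0–1] against 0 [0–0]. Median and both quartiles coincide with p < 0.05 in only 0.3 to 0.5% of runs. The fogging scale is not in the file, and the pretest rule covers continuous data, so it is not established that graded fogging would follow it. What remains is the missing effect estimate and interval.

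**Independent groups.** A rank test does not repair unequal variances. At SD 1:3 with 60 per group, the rule rejects 6.8% against about 5% for Welch's test. The cohorts differ by indication, however, so this contrast is marginal to the lens objectives.

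**Later specification.** Section 7 cites a study-specific SAP, and section 7.2.4 has the final plan agreed before data lock and analysis. This leaves time for correction, but nothing in the file replaces the rule.

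**Conclusion.** The point holds as a moderate defect of specification. For continuous endpoints the tested quantity and the reported summary depend on pretests. Bartlett's test is irrelevant to the within-eye comparison, yet it would divert about half of trials at an SD ratio of 0.77 and nearly all at 0.5. Neither route estimates the within-eye difference with a confidence interval.

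The consequence is interpretive: a p-value may refer to something other than the mean difference, most clearly when differences are skewed. It does not show that the trial's 5% level fails in general. The diversion frequencies rest on normal readings, 60 pairs and 5% pretests; the 6 to 26% rests on assumed gamma differences. The defect remains after paired tests are chosen, because the pretests would still select between them.

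**What to change.** Delete both pretests from section 7.2.1 and, before data lock and before any lens comparison is seen, name one analysis per data type:

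- **Continuous measures, such as light level if recorded on a continuous scale:** mean within-eye difference with 95% CI by paired t-test; Wilcoxon signed-rank always shown as a stated sensitivity analysis.
- **Any endpoint recorded as ordered grades:** signed-rank test, with the full grade distribution per lens and the share of eyes better, the same or worse with the new lens.
- **Any contrast of independent groups:** Welch's t-test, with the difference and 95% CI.

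State that tests are two-sided, if that is intended.

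The cost is wording only: no extra eyes, data or visits. There is one small downside. With strongly skewed differences the paired t-test can run slightly above 5% (6.8% at skewness 2), which the stated sensitivity analysis helps the reader to judge.

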### 1.1.3 Wide-angle retina viewing system

During posterior segment surgery (vitrectomy), viewing of the retina is required. For that purpose, an

additional optical system below the microscope is required.

These optical systems can be divided into two categories:

1) Contact lens systems

[figure not shown]
This lens type is placed on the corneal surface with some contact gel in between the cornea and the lens. Different lenses are being used, either with a convex surface for wide-angle viewing or with a flat (or concave) surface for high-magnification viewing. In the former lens type, an image inverter is required to generate an erect retina image for the surgeon.

Although the optical quality of these contact lenses is very good, there are several disadvantages:

- The continuous contact with the corneal surface may cause corneal lesions (epithelial defect), or cause corneal edema during prolonged surgery sometimes rendering retinal visualization impossible necessitating to discontinue the surgery.
- The lens must be kept in a horizontal position on the eye, which requires an experienced surgical assistant to stabilize the lens during surgery. In our center, the surgical assistance is performed by residents in training who rotate every 6 weeks. Hence, it is impossible to have a well-trained surgical assistant for this purpose.
- When using a wide-angle viewing lens, although an extreme wide-field angle can be obtained, this field-of view is highly limited by the pupil size. Since vitrectomy surgery is usually performed in patients >65 years of age, the pupil dilation is often limited, restricting the field-of view.

As a result, the use of a contact lens during vitrectomy surgery is only occasionally used during surgery.

[figure not shown]

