## 2 Objectives and Design

### 2.1 Study objectives and hypotheses

This study is designed to obtain more information on the efficacy of the disposable RESIGHT lenses in routine vitrectomy surgery. This information can lead to adjustments to these surgical lenses to further fine tune a device which can be used by other surgeons.

[figure not shown]
Theoretically, both the improved lens design and better resistance to fogging should improve the visualization of the retina hence facilitate the surgery, increasing the surgical safety.

During the surgery, a comparison will be done between the present lenses used (reusable RESIGHT lenses and disposable Vitreq contact lens) and the new disposable RESIGHT lenses. For that purpose, both lenses will be mounted on the rotating arm of the RESIGHT allowing the surgeon to toggle between both lenses during surgery. This toggling takes a few seconds, hence the total surgery time may be extended by ~30 seconds. However, this will most likely not impact patient safety since a vitrectomy surgery typically requires one hour time.

To compare the image generated by the present and the new RESIGHT lenses, both still shots and (short) video recordings will be created during the surgery. For this purpose, the internal camera and recording system of the ARTEVO microscope will be used. This will not have any impact on the surgery duration. Since only the retinal image is recorded, there is no risk of patient recognition on the recorded photos and videos.

Moreover, the Artevo microscope has a function that generates anonymous data export which will protect the patients' identity.

Although there is no contact between the lens and the patient, the lens is touched by the surgeons' glove, hence must be sterile. ZEISS will deliver these lenses pre-sterilized according to the present required standards. ZEISS will provide these lenses packaged and labeled according to their specifications.

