## 2.2 Primary Endpoints

The purpose of this study is to evaluate the intra-operative efficacy of new intra-operative viewing device, more specifically:

[figure not shown]
1. To determine whether the performance of the disposable MACULA LENS is comparable or even better than a flat contact lens, due to its improved resolution. For this purpose, the in-house available Vitreq contact lens will be used.  
This parameter will be determined in the macular surgery study arm only.
2. To determine that the disposable ULTRA WIDE-ANGLE LENS does not condensate / condensates to a lesser extent during surgery.  
This parameter will be determined in both study arms.
3. To determine that the disposable ULTRA WIDE-ANGLE LENS allows for imaging up to ora serrata on human eyes, reducing the need for indenting. This parameter will be determined in the retinal detachment surgery study arm only.
4. To evaluate whether both peripheral vitrectomy as well as macula work are possible with the disposable wide-angle lens. This parameter will be determined in the macular surgery study arm only.
5. To evaluate the amount of fogging that occurs when using the disposable wide-angle lens compared to using the reusable yellow lens.
6. To evaluate whether the amount of light to illuminate the retina is reduced when using any of the disposable lenses compared to the reusable yellow/green lenses. This parameter will be

determined in both study arms.

7. To evaluate whether the disposable lenses show a more natural color representation compared to the reusable yellow and green lenses. This parameter will be determined in both study arms.
8. To evaluate whether the iOCT quality recorded with the disposable macula lens is similar to or better than the iOCT recorded using the green reusable lens. This parameter will be determined in the macular surgery study arm only, where iOCT is being recorded as standard-of-care.

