### 2.3 Design of the Clinical Investigation

Investigator-initiated, academic, mono-center, prospective, interventional case study. No randomization will be performed.

Sixty eyes will be enrolled in two study arms:

- Group 1: 60 eyes that undergo primary vitrectomy surgery for retinal detachment
- Group 2: 60 eyes that undergo macular surgery: pucker, vitreomacular traction or macular hole.

The study duration for the participants starts from the moment the patient is informed.

After the surgical procedure, the surgeon will record the parameters that are required to determine the primary outcomes of the study (§6). These parameters will be recorded in a Formasa form specifically designed for this study: see attached document. No information will be collected in this document that can identify the patients, the only clinical information used is the indication of the surgery (since this impacts the primary outcome parameters collected). After all patients (120 eyes) will be included in the trial, a KWS query will be used to export the Formasa forms. Only the content of these forms will be exported for statistical analysis.

In case a device deficiency occurs (any issue that hinders the surgery when using a disposable RESIGHT lens), it will be recorded in the Device Deficiency form (see attachment). Additionally, any (Serious) Adverse Event resulting from such Device Deficiency will be recorded in the (S)AE form (see attachment).

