### 4.3 Randomization Procedure (if applicable)

Not Applicable. Two study arms will be created depending on the surgical indication.

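### Section 7.2.1 applies one between-group testing rule to lens comparisons made within the same eye: no paired test for proportions, and paired and independent-group tests mixed for continuous data

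*Combined protocol and SAP*

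**What the plan says.** Design. Section 2.1 states that during the surgery "a comparison will be done between the present lenses used (reusable RESIGHT lenses and disposable Vitreq contact lens") and the new disposable lenses, and that "both lenses will be mounted on the rotating arm of the RESIGHT allowing the surgeon to toggle between both lenses during surgery". Section 2.3 rules out randomisation. Section 4.3 adds: "Two study arms will be created depending on the surgical indication". No group of eyes is defined by lens.

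Endpoints. In Section 2.2, items 1, 5, 6, 7 and 8 set a disposable lens against a present one. Item 5 is typical: "To evaluate the amount of fogging that occurs when using the disposable wide-angle lens compared to using the reusable yellow lens". Items 2, 3 and 4 name no explicit comparator lens. No item compares retinal detachment eyes with macular eyes.

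Analysis. Section 7.2.1 covers all endpoints and is framed as comparing groups.
- Continuous data: t-test or ANOVA if Bartlett's and Shapiro-Wilk tests are passed, otherwise Wilcoxon signed rank or Kruskal-Wallis.
- Proportions: "for count data, the Pearson Chi-Squared test will be performed to compare proportions".

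Section 7.2.2 sets the level at 5% without saying one- or two-sided. Section 7 adds that "a detailed description of the analysis is provided in the study-specific Statistical Analysis Plan (SAP"), and Section 7.2.4 leaves the final plan to be agreed before lock.

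**The concern.** Two lenses judged in one eye, by one surgeon, in one operation give related observations. The two-sample Pearson test treats them as coming from different eyes: it uses only the two marginal proportions and ignores how the ratings line up eye by eye. Its standard error is then wrong whenever the ratings correlate.

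The continuous rule has a related fault. Bartlett's test and Kruskal-Wallis belong to independent groups, signed rank belongs to pairs, and the t-test is not assigned to either. Two analysts following Section 7.2.1 could reach different p-values from the same data.

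What is at stake is whether the p-values on the lens endpoints mean what the 5% level says, and whether a real difference between lenses is missed.

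**Working it through.** **Step 1. Is the contrast within eye?** Sections 2.1, 2.3 and 4.3 read together say yes for items 1, 5, 6, 7 and 8. For item 1 the toggle is not the reason, since a contact lens is not on the rotating arm: "This lens type is placed on the corneal surface with some contact gel in between the cornea and the lens" (Section 1.1.3). There the pairing rests on the general sentence in Section 2.1.

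**Step 2. What does the form record?** Section 2.3 says "the surgeon will record the parameters that are required to determine the primary outcomes of the study". Section 8 describes the matching eCRF instrument only as a report on the disposable lenses used. The form itself (Appendix 4) is not in the text available. Two layouts are possible, a score per lens or one comparative rating per eye, and they need different tests.

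**Step 3. A score per lens.** From the documents: 60 eyes per arm and a 5% level. The plan gives no power, rate or effect size to reproduce; only 2 × 60 = 120 can be checked. Assumed: two-sided testing, the rates, and the within-eye correlation φ.

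With the same true rate p on both lenses:
- true variance of the difference = 2p(1−p)(1−φ)/n
- variance used by Pearson = 2p(1−p)/n

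Pearson's statistic is therefore too small by a factor √(1−φ), and its approximate type I error is 2[1−Φ(1.96/√(1−φ))]. At φ = 0.3, 1.96/0.837 = 2.34, giving 1.9%. At φ = 0.5, 1.96/0.707 = 2.77, giving 0.6%. At φ = −0.3, 1.96/1.140 = 1.72, giving 8.6%.

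Exact enumeration of all paired tables agrees (60 eyes, Pearson without continuity correction):

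| φ | Pearson type I error, 70% on both | Mid-p McNemar type I error | Power 60% v 80%: Pearson | Mid-p McNemar | Exact McNemar |
|---|---|---|---|---|---|
| 0 | 5.2% | 4.4% | 68% | 65% | 59% |
| 0.1 | 4.1% | 4.5% | 69% | 70% | 63% |
| 0.3 | 2.1% | 4.7% | 71% | 81% | 76% |
| 0.5 | 0.65% | 4.4% | 75% | 94% | 90% |

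At φ = −0.3 Pearson's type I error is 8.9%.

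Items 6 and 7 use both arms. With 120 eyes, 65% against 80% and φ = 0.1/0.3/0.5, power is 76/79/83% for Pearson and 78/87/96% for mid-p McNemar. For 60% against 80% the loss is small: 94/96/98% against 95/98/99.9%.

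**Step 4. One data set, two answers.** Suppose 39/60 are adequate with the present lens and 48/60 with the new one.
- Pearson: pooled rate 87/120 = 0.725; statistic 0.15² / (0.725 × 0.275 × 2/60) = 3.39; p = 0.066 whatever the pairing.
- Exact McNemar: p = 0.035 if the discordant eyes split 12 to 3, and p = 0.078 if they split 15 to 6.

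Pearson cannot tell these two cases apart.

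**Step 5. Continuous scores.** Only if the t-test is run unpaired: for a 0.4 SD difference, 60 eyes and correlation 0.1/0.3/0.5, simulated power is 59/60/62%, against 62/73/86% for the paired test.

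**Step 6. One comparative rating per eye.** There is no paired table, and Steps 3 to 5 do not apply. The question becomes whether the split departs from even. For 37 against 23 of 60, a one-sample chi-squared gives statistic (7² + 7²)/30 = 3.27, p = 0.071; a sign test gives p = 0.092. Section 7.2.1 does not say that a one-sample version is meant.

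**The case against.** The strongest reply has four parts.

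- **The form is unknown.** The loss of the 5% level needs a separate score per lens and a non-zero correlation, and no section states either. This stands, and it limits the impact claim. It does not make the rule fit: neither layout calls for a two-sample comparison of lenses.
- **Some listed methods could serve.** Signed rank suits paired scores or a comparative rating tested against no difference, and chi-squared has a one-sample form. A reader might infer that with one rating per eye every listed test fails, or that false positives rise. The documents do not support that, because Section 7.2.1 prescribes no layout that sets the two preference counts against each other as independent samples.
- **Part of the rule is legitimate.** Chi-squared, ANOVA and Kruskal-Wallis would fit a summary by indication, and the t-test is not said to be unpaired. A reader might infer that an unpaired t-test is prescribed; it is neither stated nor ruled out. For continuous data the fault is inconsistency.
- **Detail is deferred.** The SAP cited in Section 7 may name paired tests. Its text is not available here, so this point concerns Section 7.2.1 alone, which would still have to agree with that SAP.

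It is also fair that the documents do not say every lens contrast is made in every eye, that the study aims at information for refining the lenses, and that at correlation 0.1 the mid-p gain is one percentage point.

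**Conclusion.** The point holds as a mismatch between design and analysis text. For yes/no lens contrasts no paired method is named and the one test given is a between-group test as framed. For scores, paired and independent-group methods are mixed. It should be fixed.

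The size is conditional. With separate lens scores and positive correlation, which is likely when ratings share an eye, surgeon and operation, Pearson is conservative. In one arm of 60 eyes the power lost against mid-p McNemar, for 60% against 80%, runs from about 1 point at correlation 0.1 to 10 at 0.3 and 19 at 0.5. A reader might infer that the plan inflates false positives; that needs negative correlation, which is less plausible. All rates and correlations are assumptions. With one comparative rating per eye, the gap is an unspecified one-sample method and no error rate can be attached to it.

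Confidence is high on what Section 7.2.1 says and medium on its consequence.

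**What to change.** In Section 7.2.1, and identically in the final statistical plan, state that lens contrasts are within eye, and assign tests by data type:
- **Yes/no score per lens:** McNemar (mid-p or exact, chosen in advance) with a confidence interval for the paired difference.
- **Numeric score per lens:** paired t-test or Wilcoxon signed rank on within-eye differences, without the Bartlett gate.
- **One comparative rating per eye:** a sign test or another named one-sample test.
- **Contrasts between the two indications:** keep chi-squared, ANOVA and Kruskal-Wallis.

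The cost is wording plus one check of the form's layout. No patients or data are added, and Section 7.2.4 leaves room for it before lock.

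The drawback is that near zero correlation the paired tests gain nothing. At 0, mid-p McNemar has 65% power against 68% for Pearson; at 0.1, exact McNemar has 63% against 69%.
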